10.1.2.1 Ethanol and PSL (Part A)

The similarity of PD parameters between treatments will be analyzed using the model specified in [Section 10.1.2](#), where treatment includes Ethanol, Placebo, PSL+Ethanol and PSL+ Placebo.

The following contrasts will be calculated within the model:

- PSL+Ethanol (Treatment Period 4/5: Day 5/7) vs PSL+Placebo (Treatment Period 4/5: Day 5/7) (primary comparison)
- PSL+Placebo (Treatment Period 4/5: Day 5/7) vs Placebo (Treatment Period 1/2: Day 1)
- Ethanol (Treatment Period 1/2: Day 1) vs Placebo (Treatment Period 1/2: Day 1)
- PSL+Ethanol (Treatment Period 4/5: Day 5/7) vs Ethanol (Treatment Period 1/2: Day 1)

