3 OBJECTIVES AND ENDPOINTS

The objectives and corresponding endpoints for this study are presented in [Table 3-1](#).

Table 3-1: Study objectives and endpoints

Objectives	Endpoints
Primary	

 Part A: To evaluate the PD interaction between steady-state treatment with PSL and ethanol 	
 Smooth pursuit (%) to assess eye movement coordination and attention

 Part B: To evaluate the PK interaction between steady-state treatment with PSL and CBD 	
 $C_{max,ss}$ and AUC_{τ} obtained from the plasma concentration-time profiles for PSL and CBD
Secondary	

 Part A: To evaluate the PK interaction between steady-state treatment with PSL and ethanol 	
 Ethanol dose infused over time $C_{max,ss}$ and AUC_{τ} obtained from the plasma concentration-time profiles for PSL

 Part B: To evaluate the PK interaction between steady-state treatment with PSL and CBD 	
 $t_{1/2}$, and $CL_{ss/F}$ obtained from the plasma concentration-time profiles for PSL and CBD

 Parts A and B: To evaluate the PD interaction between steady-state treatment with PSL and ethanol or between steady-state treatment with PSL and CBD 	
 Smooth pursuit (%) to assess eye movement coordination and attention (Part B only) Saccadic peak velocity (degrees/sec) to assess sedation Adaptive tracking (%) to assess visuo-motor control and vigilance Body Sway to assess postural stability

 Parts A and B: To evaluate the safety and tolerability of PSL in study participants receiving concomitant ethanol or CBD 	
 Adverse events (AEs), serious adverse events (SAEs), treatment-related AEs, and AEs leading to discontinuation of the study
Other	

 Parts A and B: To evaluate the safety and tolerability of PSL in study participants receiving concomitant ethanol or CBD 	
 Vital signs (pulse rate, respiratory rate, systolic blood pressure [SBP], and diastolic blood pressure [DBP]) 12-lead electrocardiogram (ECG) parameters Physical examination findings Clinical laboratory test results (hematology, clinical chemistry, and urinalysis)

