9.4.1 Ethanol and PSL (Part A)

The similarity of the PD parameters between treatments with ethanol and without ethanol (ethanol placebo alone, ethanol alone, PSL with ethanol placebo, PSL with ethanol) will be analysed separately by a mixed model of analysis of variance (ANOVA) with treatment, sequence, period, time, and treatment by time as fixed effects; with subject, subject by treatment, and subject by time as random effect; and with the (average) Baseline value as covariate. The primary comparison is PSL with ethanol vs PSL alone. The other comparisons will be: PSL alone vs ethanol placebo, ethanol alone vs ethanol placebo alone, and PSL with ethanol vs ethanol alone. Different contrasts (with estimate difference and 95% confidence interval [CI]) from ANOVA will be defined for each of these comparisons.

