2 PROTOCOL SUMMARY

2.1 Study objectives and endpoints

2.1.1 Part A

Objectives	Endpoints
Primary	
To evaluate the PD interaction between steady-state treatment with PSL and ethanol	
 Smooth pursuit (%) to assess eye movement coordination and attention
Secondary	
To evaluate the PK interaction between steady-state treatment with PSL and ethanol	
 Ethanol dose infused over time $C_{max,ss}$ and AUC_{τ}, obtained from the plasma concentration-time profiles for PSL and its metabolites
To evaluate the PD interaction between steady-state treatment with PSL and ethanol	
 Saccadic peak velocity (degrees/sec) to assess sedation Adaptive tracking (%) to assess visuo-motor control and vigilance Body Sway to assess postural stability
To evaluate the safety and tolerability of PSL in study participants receiving concomitant ethanol	
 Adverse events (AEs), serious adverse events (SAEs), treatment-related AEs, and AEs leading to discontinuation of the study

Other	
To evaluate the safety and tolerability of PSL in study participants receiving concomitant ethanol	
 Vital signs (pulse rate, respiratory rate, systolic blood pressure [SBP], and diastolic blood pressure [DBP]) 12-lead electrocardiogram (ECG) parameters Physical examination findings Clinical laboratory test results (hematology, clinical chemistry, and urinalysis)
To evaluate the PD interaction between steady-state treatment with PSL and ethanol	
 Visual analogue scales (VAS) Bond & Lader to assess alertness, mood, and calmness VAS feeling high, internal and external perception (Bowdle) VAS for alcohol intoxication to assess the effects of ethanol
To evaluate the PK interaction between steady-state treatment with PSL and ethanol	
 t_{max} and C_{trough} obtained from the plasma concentration-time profiles for PSL and its metabolites
To collect and store blood for potential ADME genotype (if needed)	
 Possible ADME genotyping for drug metabolizing enzymes (depending on the outcome of PSL (and metabolite) PK analyses)
To collect urine samples for additional PK analyses depending on the outcome of PSL (and metabolite) PK analyses, if needed	
 Urine sample PK analysis

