2.2.2 Part A

Treatment Periods 1 and 2, and 4 and 5 are 2-way cross-over, placebo-controlled, ethanol-clamping periods with a washout of at least 2 days between Treatment Periods 2 and 3; PSL is not administered in Treatment Periods 1 and 2. Treatment Period 3 is an open-label PSL up-titration period toward a maintenance level of 200mg BID and is immediately followed by Treatment Period 4 and Treatment Period 5. Treatment Period 6 is the PSL tapering open-label period. A detailed schematic diagram of Part A of the study is provided in Figure 2-1.

The objectives of Part A are to evaluate the: plasma PK, safety and tolerability of PSL and its metabolites in the presence and absence of ethanol; metabolizing capacity of ethanol in the presence and absence of PSL; effect of PSL on PD parameters in the presence and absence of ethanol; effect of ethanol on PD parameters in the presence and absence of PSL.

Figure 2-1: Study schematic – Part A

BID=twice daily; CBD=cannibidiol; D=day; FU=Follow-up Period; PBO=placebo; PSL=padsevonil; W=week

Note: Follow up will occur between 7 to 10 days after the final dose of PSL.

Note: A WO of at least 2 days will occur between Treatment Period 2 and Treatment Period 3.

Study participants will be randomized to one of four treatment sequences:

Table 2-2: Treatment Sequences – Part A

Sequence ID	Randomization Sequence	Sequence in Full
1	Ethanol(TP1)/Placebo(TP2)/ Ethanol(TP4)/Placebo(TP5)	Ethanol (TP1)/Placebo (TP2)/PSL(TP3)/ PSL+Ethanol (TP4)/PSL+Placebo (TP5)/PSL(TP6)
2	Ethanol(TP1)/Placebo(TP2)/ Placebo(TP4)/Ethanol(TP5)	Ethanol(TP1)/Placebo(TP2)/PSL(TP3)/ PSL+Placebo (TP4)/PSL+Ethanol(TP5)/ PSL(TP6)
3	Placebo(TP1)/Ethanol(TP2)/ Ethanol(TP4)/Placebo(TP5)	Placebo(TP1)/Ethanol(TP2)/PSL(TP3)/ PSL+Ethanol(TP4)/PSL+Placebo(TP5)/PSL(TP6)
4	Placebo(TP1)/Ethanol(TP2)/ Placebo(TP4)/Ethanol(TP5)	Placebo(TP1)/Ethanol(TP2)/PSL(TP3)/ PSL+Placebo(TP4)/PSL+Ethanol(TP5)/ PSL(TP6)

TP=Treatment Period.

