9.1.2.1 Ethanol interaction on PSL (Part A)

The log-transformed PK parameters ($C_{\max,ss}$, AUC_{τ}) of PSL and its metabolites will be analyzed separately by a mixed ANOVA with period (Treatment Period 4 and 5) and treatment (PSL+Ethanol and PSL+Placebo) as fixed effects and study participant as the random effect to assess the effects of ethanol on PSL.

Point estimates for the ratio of geometric means with and without ethanol (PSL+Ethanol vs PSL+Placebo) and the respective 2-sided 90% CIs will be computed using the least squares means and the root mean squares of error from the mixed effects model, based on the log-transformed data with subsequent exponential transformation.

Lack of ethanol effect on PSL will be concluded if the 90% CI of the ratio between PSL+Ethanol and PSL+Placebo of the least squares means for the log transformed AUC_{τ} , and $C_{\max,ss}$ is within the conventional acceptance range of 80% to 125%.

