10.1.1 Descriptive figures and summaries

The PD parameters (absolute values and changes from baseline) will be summarized by phase, treatment and timepoint using descriptive statistics (number of available observations [n],

arithmetic mean, median, SD, minimum, maximum, geometric mean, geometric CV and 95% CI for the geometric mean [assuming lognormally distributed data]).

Individual participant profiles of PD parameters over time will be generated using the FAS.

Graphs of the Least Squares Means estimates over time by treatment will be presented with 95% confidence interval (CI) as error bars.

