10.1.2 Statistical analysis of pharmacodynamics variables

For the analysis of PD variables, there will be two baselines per study participant (Kenward-Rogers, 2010):

1. Between subject baseline = mean of all predose PD parameter for each subject
2. Within subject baseline = baseline at given day – between subject baseline

The PD parameters will be analyzed separately by a repeated measures ANOVA with treatment, time, treatment by time, period and sequence as fixed effects; time as repeated measure; with subject by period and subject as random effects and within subject baseline and between subject baseline and the baseline interactions with time as covariates. [Section 10.1.2.1](#) and [Section 10.1.2.2](#) specify which treatments to include in the model.

Due to the confounding of treatment within period within the design only the periods of interest will be included in any given comparison. For example, if the comparison is within the interaction phase then only Periods 4 and 5 will be kept in the model.

Period should be removed from the model statement due to confounding with treatment in any comparisons where either test or reference period only contains one treatment option. It will be left in the repeated statement as period is synonymous with treatment.

The following SAS code may be used for the repeated measures ANOVA stated above:

Contrasts for each PD variable will be reported along with 95% CI. Variables will initially be analyzed without transformation, but if visual inspection of the residual plots suggest otherwise (data are not normally distributed), an appropriate transformation may be applied.

Further exploratory analyses for PD variables may be conducted by UCB.

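### Part A's primary objective is the PSL–ethanol PD interaction, but the plan lists four simple-effect contrasts and no difference of differences with a confidence interval

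*SAP*

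**What the plan says.** Protocol Table 3-1 gives one primary objective for this part: "Part A: To evaluate the PD interaction between steady-state treatment with PSL and ethanol". Its endpoint is smooth pursuit (%). SAP 2.1.1 repeats both.

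Protocol 9.4.1 then states: "The primary comparison is PSL with ethanol vs PSL alone". SAP 10.1.2.1 names the same primary contrast, "PSL+Ethanol (Treatment Period 4/5: Day 5/7) vs PSL+Placebo (Treatment Period 4/5: Day 5/7) (primary comparison", and three others: PSL+Placebo vs Placebo, Ethanol vs Placebo, and PSL+Ethanol vs Ethanol. Each is reported with a 95% CI. The only interaction terms in the SAP 10.1.2 model are treatment by time and baseline by time.

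Three other passages bear on the point:
- SAP 2.2.2 lists the Part A aims, among them the "effect of ethanol on PD parameters in the presence and absence of PSL" and the corresponding effect of PSL with and without ethanol.
- SAP 10.1.2 restricts each comparison to its own periods; for example, "if the comparison is within the interaction phase then only Periods 4 and 5 will be kept in the model".
- SAP 2.3 bases 22 participants on a 3.96-point ethanol effect. It says the expected size of the interaction is unknown, but that 3.96 points could similarly be detected for PSL+Ethanol vs PSL+Placebo.

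**The concern.** The primary contrast is the ethanol effect under PSL. Smooth pursuit was chosen because SAP 2.3 regards it as the CNS variable most sensitive to ethanol, so this contrast is expected to differ from zero even if PSL leaves the ethanol effect unchanged. A primary contrast of 3.96 points of impairment would mean additivity if ethanol alone also costs 3.96 points, potentiation if it costs 1.98, and attenuation if it costs 7.92. The contrast has the same value in all three cases.

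Contrast 3 (Ethanol vs Placebo) lets a reader subtract, and SAP 10.1.1 adds a picture: "Graphs of the Least Squares Means estimates over time by treatment will be presented with 95% confidence interval (CI) as error bars". Neither gives the precision of the difference. As planned, Part A can report the ethanol effect with and without PSL. It cannot say, with a stated uncertainty, whether the two differ.

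**Working it through.** **1. The plan's own figure.** Inputs from SAP 2.3: n = 22, difference 3.96, SD of difference 6.0, paired t-test, two-sided 0.05. The non-centrality is 3.96 × √22 / 6.0 = 3.10 on 21 degrees of freedom, and power is 83.9%. The smallest n reaching 80% is 21, so the stated 22 reproduces and its 80% is slightly conservative. For this simple contrast the 95% CI half-width is 2.08 × 6.0 / √22 = 2.66 points, and the difference detectable with 80% power is 3.76.

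**2. Is the interaction among the four contrasts?** Order the cells as Placebo, Ethanol, PSL+Placebo, PSL+Ethanol.

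| Contrast | Coefficients |
|---|---|
| 1. PSL+Ethanol vs PSL+Placebo (primary) | 0, 0, -1, 1 |
| 2. PSL+Placebo vs Placebo | -1, 0, 1, 0 |
| 3. Ethanol vs Placebo | -1, 1, 0, 0 |
| 4. PSL+Ethanol vs Ethanol | 0, -1, 0, 1 |
| Difference of differences | 1, -1, -1, 1 |

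The last row is contrast 1 minus contrast 3, and also contrast 4 minus contrast 2. None of the four equals it.

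**3. Can its CI be rebuilt?** Var(contrast 1 − contrast 3) = Var(1) + Var(3) − 2 Cov(1, 3). The two planned CIs give the variances but not the covariance. With a common SD of 6.0 for the two ethanol effects and within-participant correlation r, the SD of the difference is 6.0 × √(2(1 − r)).

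**4. Size.** The correlation r is not in the documents, so a range is shown. The equal SD of 6.0 is an assumption, and single paired differences stand in for the repeated-measures model. n = 22.

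| r | SD | 95% CI half-width | Detectable, 80% power | Power at 3.96 |
|---|---|---|---|---|
| -0.25 | 9.49 | 4.2 | 5.9 | 46% |
| 0 | 8.49 | 3.8 | 5.3 | 55% |
| 0.25 | 7.35 | 3.3 | 4.6 | 67% |
| 0.5 | 6.00 | 2.7 | 3.8 | 84% |
| 0.75 | 4.24 | 1.9 | 2.7 | 99% |

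At r = 0.5 the precision equals that of the simple contrast; above that it is better. The detectable interaction is 3.96 points at r of about 0.44.

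**5. Can it be fitted?** A rank check used the four sequences of SAP 2.2.2, with treatment, period and sequence as fixed effects.
- Periods 1, 2, 4 and 5 together: contrasts 1 and 3 and the difference of differences are estimable. Contrasts 2 and 4 are not, because PSL is given only in the later periods and its effect is aliased with period.
- Periods 4 and 5 alone: the difference of differences is not estimable, because the cells without PSL are absent.

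**The case against.** The strongest reply is that nothing contradicts anything. Both documents use the word interaction for two-treatment comparisons; the PK section titled "Ethanol interaction on PSL (Part A") is one. Part B uses the same wording although it has no drug-free cell in its comparisons. The four PD contrasts match the SAP 2.2.2 aims, the protocol and SAP agree on the primary comparison, and no statement on additivity is planned. All of this stands. A reader might infer that the objective obliges the sponsor to test a difference of differences, or that the primary contrast is wrong. The documents support neither.

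SAP 10.1.2 also allows further exploratory PD analyses. That permits the missing contrast but does not prespecify it. The SAS code announced there is not visible in the public copy, but the written list of contrasts is explicit.

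The periods rule is a conditional point. SAP 10.1.2.1 speaks of contrasts within a model holding all four treatments, so a four-period fit may be intended. The interaction is lost only if the primary comparison is fitted on Periods 4 and 5 alone.

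Finally, SAP 2.3 already ties its second mention of 3.96 points to PSL+Ethanol vs PSL+Placebo. The wording asked for there is a clarification, because the same sentence also speaks of the interaction.

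None of this supplies an estimate with a CI for the quantity that would separate additivity from potentiation or attenuation.

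**Conclusion.** The point holds as a gap in what is planned. The four contrasts are valid and meet the SAP 2.2.2 aims, but none estimates the departure from additivity, and its CI cannot be recovered from the planned contrast CIs. Part A measures all four cells in each participant, so the estimate can be had from data already scheduled. Severity is minor to moderate.

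The precision figures rest on an assumed r, an equal SD of 6.0 for both ethanol effects, and paired differences. A reader might infer that the trial is underpowered for the interaction. That does not follow: precision may be worse or better than for the simple contrast, depending on a correlation the documents do not give. At r = 0 the half-width (3.8) nearly equals the assumed ethanol effect (3.96), so the added contrast may not settle the question.

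**What to change.** 1. **SAP 10.1.2.1.** Add one prespecified supportive contrast, (PSL+Ethanol − PSL+Placebo) − (Ethanol − Placebo), with estimate and 95% CI, summarised over time as for the primary comparison. Fit it in its own model with Periods 1, 2, 4 and 5 and period as a fixed effect, and exempt it from the periods-of-interest rule in SAP 10.1.2. Keep the four existing contrasts in their currently planned models, since contrasts 2 and 4 cannot be estimated in the new one.
2. **Scale and assumption.** Report this contrast in raw percentage points, also when a transformation is used. State the assumption that the ethanol effect does not drift between Periods 1/2 and 4/5. A learning effect that shifts all scores equally cancels.
3. **SAP 2.3.** Add that the 3.96 points applies to the simple difference and not to the interaction contrast.
4. **Interpretation.** Rest any statement on additivity, potentiation or attenuation on this contrast, and note that a CI including 0 does not establish additivity.

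Alternative: restate the primary objective in Protocol Table 3-1 and SAP 2.1.1 as the effect of ethanol added to PSL, and draw no conclusion on additivity.

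The first route costs SAP wording, one model and one contrast, with no new data. Its drawbacks are possibly lower precision than the simple contrast and the no-drift and scale assumptions. The alternative costs only wording but gives up the additivity question.

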10.1.2.2 CBD and PSL (Part B)

The similarity of the PD parameters between treatment will be analyzed using the model specified in [Section 10.1.2](#), where treatment includes CBD, PSL, CBD+PSL and CBD+Placebo.

The following contrasts will be calculated within the model:

- CBD+PSL (Treatment Period 4/5: Day 5) vs PSL (Treatment Period 2: Day 5) (primary comparison)
- CBD+PSL (Treatment Period 4/5: Day 5) vs CBD (Treatment Period 3: Day 16)
- CBD+PSL (Treatment Period 4/5: Day 5) vs CBD+Placebo (Treatment Period 4/5: Day 5)

This analysis will also be performed for PD variables measured in Treatment Period 4/5, Day 1. Any treatment effect may be compounded by time in the first and second comparison stated above. Additionally, there may be a learning effect due to study participants performing the PD assessments multiple times.

11 SAFETY ANALYSES

All safety summaries and listings will be performed using the SS.

11.1 Extent of exposure

Administration of treatments will be listed by study participant. For PSL and CBD, the listing will include the date and time of administration of the morning and evening dose, and total daily dose. For ethanol infusion, the listing will include the date of infusion, start and stop time of infusion, duration of infusion and total volume of ethanol given.

Exposure data will be listed only.

11.2 Adverse events

All AEs will be coded using the MedDRA® and characterized as pre-treatment and treatment emergent according to the intake of each treatment. Adverse events with a start date prior to the first dose of treatment will be defined as pre-treatment AEs. A treatment-emergent AE (TEAE) is defined as any AE with a start date/time on or after the first dose of treatment or any unresolved event already present before administration of treatment that worsens in intensity following exposure to the treatment.

Adverse events will be attributed to the most recent treatment received. Adverse events that occur during the washout periods will be assigned as treatment emergent with regards to the treatment of the previous period.

The number and percentage of participants who experience TEAEs will be summarized by MedDRA SOC, PT and treatment.

Summaries of TEAEs will include the following:

- Incidence of overall TEAEs (overview including number and percentage of study participants with any TEAEs, serious TEAEs, discontinuations due to TEAEs, drug-related TEAEs, severe TEAEs and TEAEs leading to death; event counts will also be included)
- Incidence of TEAEs
- Incidence of TEAEs by maximum intensity
- Incidence of TEAEs by relationship
- Incidence of non-serious TEAEs above reporting threshold of 5% of study participants

Additional summary tables of fatal, serious and discontinuations due to TEAEs by relationship will be produced if more than one of these events occurs.

Summary tables will contain counts of study participant, percentages of study participants in parentheses and the number of events where applicable. A participant who has multiple events in the same SOC and PT during a given treatment will be counted only once in the participant counts for that treatment, but all events will be included.

In summaries including relationship, the following relationships will be summarized: 'Not related', 'Related'. Participants who experience the same event multiple times will be included in the most related category for tabulations by maximum relationship. Events with missing relationship will be considered as 'Related' but recorded as missing in the listings.

In summaries including intensity, the following intensity categories will be summarized: 'Mild', 'Moderate', 'Severe'. Participants who experience the same event multiple times will be included in the most severe category for tabulations by maximum intensity. Events with missing intensity will be considered as 'Severe' events for summary purposes but recorded as missing in the listings.

Adverse event summaries will be ordered alphabetically by SOC and decreasing frequency of PT within SOC in the group column for tables including event counts. For tables including only number and percentage of study participants, summaries will be ordered alphabetically by SOC and decreasing incidence of PT within SOC in the group column.

Listings of AEs and TEAEs will include the following:

- All AEs
- Incidence of all TEAEs
- All Serious AEs
- Discontinuation due to AEs

All listings (except incidence of all TEAEs) will be presented by study participant and treatment sequence and will include the onset date/time and outcome date/time of the event, most recent treatment received, the event duration (derived), time to onset (derived), pattern of event, intensity, relationship, action taken, outcome and AEs that led to discontinuation, TEAEs and SAEs will be flagged.

The listing of incidence of all TEAEs will be presented by treatment and will include intensity, relationship, severity, number of study participants reporting at least one TEAE within SOC/PT, number of individual occurrences of TEAE and site-study participant number.

